9.7.1 Effectiveness and Health Economic Analysis

A Pearson's Chi-Squared test will be used to compare the incidence of successful LAA exclusion between the two procedure groups. Alternatively, a Fisher's Exact test will be used if justified by small cell counts (less than 5) and Clopper-Pearson (Exact) 95% CI will also be reported.

In addition, LAA exclusion might also be analyzed using multiple logistic regression model with the proportion of the event of successful LAA exclusion as the dependent variable and the following independent variables: sites (or clusters of sites), surgical approach (sternotomy, right mini-thoracotomy or other), age, gender, CHA2DS2- VASc score, HASBLED score and relevant interaction terms.

Study Number: CP2015-2 CONFIDENTIAL Page 36 of 48

Healthcare resource use will be assessed by examining either total resource use, treatment costs or formal cost effectiveness/cost utility analysis. Resource use such as hospital length of stay, OR time, and total treatment costs will be compared between the treatment groups using a two-way analysis of variance (ANOVA) model with procedure group (AtriClip LAA Closure or anticoagulation therapy and without AtriClip LAA Closure) and site as fixed effects in the model.

These endpoints will also be compared using the two-sided t-test. A Shapiro-Wilk test of normality will be performed and if the normality assumption is not met, an approximate non-parametric model (e.g. Wilcoxon rank-sum test) may be performed.

A Pearson's Chi-Squared test will be used to compare difference in 30 day readmits, number of neurological consults, additional procedures, and patient medication use between the two procedure groups.

Formal economic models utilizing treatment effectiveness (Quality adjusted life years, costs to reduce stroke, etc.) may be built with collected data and other secondary sources accounting for specific country perspective and discounted appropriately.

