5.2 Left Atrial Appendage (LAA) Exclusion (Index Procedure)

5.2.1 No AtriClip arm

If the subject is randomized to the no AtriClip arm, the left atrial appendage should be left intact with no management.

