9.6 Analysis Populations

Intent-To-Treat (ITT) Population: The effectiveness, safety, health economic and Qualify of life analyses will be based on the ITT population. The ITT Population is defined as all subjects randomized to either the AtriClip LAA Closure or anticoagulation therapy and without AtriClip LAA Closure group and on whom the surgical index procedure is attempted (even if the index procedure is aborted).

POAF Diagnosis (POAF) Population: This population will include all ITT subjects diagnosed with POAF. This will be the primary analysis population for effectiveness and health economic endpoints.

Per-Protocol (PP) Population: A PP population may be defined for effectiveness, health economic and Quality of Life analyses. This population is defined by POAF population but without any major protocol violations, that is, those that could potentially bias the results.

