9.7 Analysis of Study Endpoints

Study endpoints will be summarized by treatment group and overall as appropriate. Continuous variables will be summarized by presenting the number of subjects, mean, standard deviation, median, minimum, maximum by procedure group (AtriClip LAA Closure or anticoagulation therapy and without AtriClip LAA Closure). Tabulation of categorical variables by group will include counts and percentages. 95% confidence intervals will be provided as appropriate.

Since this is an exploratory study, additional analyses, additional analysis populations, covariates and summary tables and/or graphs will be generated as needed.

In all analyses described below, the null hypothesis will be a two-sided test of no treatment group difference. All statistical tests will use a two-sided significance level of α =0.05.

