9.7.2 Safety Analysis

A Pearson's Chi-Squared test will be used to compare the incidence of complications associates with LAA exclusion between the two procedure groups. Alternatively, a Fisher's Exact test will be used if justified by small cell counts (less than 5) and Clopper-Pearson (Exact) 95% CI will also be reported. Thromboembolic and hemorrhagic events will be similarly analyzed.

In addition, complications associated with LAA exclusion and thromboembolic/hemorrhagic might also be analyzed using multiple logistic regression model similar to the effectiveness endpoint (successful LAA exclusion) described above.

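### The planned between-arm test of successful LAA exclusion cannot inform on device performance, and section 9.6 is inconsistent about the primary population for this endpoint

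*Combined protocol and SAP*

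**What the plan says.** Endpoint 2 (section 3.0) is intraoperative success of LAA exclusion: no flow between appendage and atrium and a remnant of at most 5 mm, judged by TEE with Doppler during the operation. Section 9.7.1 uses a Pearson chi-squared test to "compare the incidence of successful LAA exclusion between the two procedure groups", with Fisher's exact test as the alternative when cell counts fall below 5. It adds that "Clopper-Pearson (Exact) 95% CI will also be reported". Section 9.7 sets the frame for all tests: "the null hypothesis will be a two-sided test of no treatment group difference", at the 0.05 level. It also says that "Tabulation of categorical variables by group will include counts and percentages".

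For the control arm, section 5.2.1 states that "the left atrial appendage should be left intact with no management".

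On populations, section 9.6 opens by placing effectiveness, among other analyses, on the ITT population. That population is the randomised subjects in whom the index procedure was attempted. The section then defines the POAF population as the ITT subjects diagnosed with POAF and says: "This will be the primary analysis population for effectiveness and health economic endpoints". Section 9.7.2 refers back to exclusion as "the effectiveness endpoint (successful LAA exclusion"). Section 4.1 places the development of POAF in the hospital stay, after the operation.

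**The concern.** There are two separate problems.

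First, an appendage that nobody has touched is not expected to show zero flow and a remnant of 5 mm or less. With adherence, the control proportion is therefore about 0% by design, and a null hypothesis of equal proportions is false as soon as the clip works in a handful of patients. A reader of the final report would see p < 0.001 beside an effectiveness endpoint and might take it as evidence of good closure. The same p < 0.001 would be printed for a poor device.

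Second, the ITT sentence and the POAF-primary sentence of section 9.6 point to different sets for this endpoint. The one labelled primary is selected by a diagnosis made after the outcome has been recorded. Every clip subject assessed by intraoperative TEE has the outcome, whatever rhythm follows, so restricting the primary estimate costs precision, and the plan gives no reason for it.

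**Working it through.** **Inputs.** Section 9.4 gives about 1333 AtriClip and 667 control subjects and a 40% POAF rate. The expected POAF set is 0.40 × 2000 = 800, split 2:1 into 533 and 267, which agrees with the figures stated there. The pre-attrition 533 is the right number here, because an intraoperative outcome is not lost to follow-up. The documents give no expected exclusion rate and no power for this endpoint, so all success rates below are assumptions shown as a range. The 1333 stands in for the AtriClip arm of the ITT population, which could be slightly smaller.

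**Where the planned test rejects.** Let k be the clip-arm successes, with zero in controls. Under the null, the chance that all k fall in the clip arm is C(n_clip, k) / C(N, k). For k = 9 in the POAF set this is C(533, 9) / C(800, 9) = 0.0253. Adding the opposite-tail tables that are no more probable gives the two-sided Fisher p-value.

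| Set | k | Success | Fisher p | Pearson p |
|---|---|---|---|---|
| POAF, 533 vs 267 | 8 | 1.5% | 0.057 | 0.044 |
| POAF, 533 vs 267 | 9 | 1.7% | 0.033 | 0.033 |
| All randomised, 1333 vs 667 | 8 | 0.6% | 0.058 | 0.045 |
| All randomised, 1333 vs 667 | 9 | 0.7% | 0.034 | 0.033 |

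The zero control cell is below 5, so the small-cell rule of section 9.7.1 points to Fisher and the threshold is 9.

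**Chance of rejecting with a failing device.** In the POAF set this is P(Bin(533, s) ≥ 9). It is 0.739 at s = 2%, 0.979 at s = 3% and above 0.999 at s = 5%.

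**Can the p-value separate a poor device from a good one?** With zero control successes, Pearson's statistic is N·k·n_ctrl / [n_clip·(N − k)].
- 50% success (266/533): 800 × 266 × 267 / (533 × 534) = 199.6, p about 3 × 10⁻⁴⁵.
- 95% success (506/533): 800 × 506 × 267 / (533 × 294) = 689.7, p about 5 × 10⁻¹⁵².

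Both print as p < 0.001.

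**Does control non-adherence change this?** Suppose, as an assumption, that 13 of 267 controls (5%) counted as successes. Fisher then rejects from 47/533 (8.8%, p = 0.047), which is still far too low a bar to say anything about closure.

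**Precision by population.** Clopper-Pearson 95% limits for x of n are the 2.5% quantile of Beta(x, n − x + 1) and the 97.5% quantile of Beta(x + 1, n − x). Half-widths are in percentage points.

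| Assumed success | POAF, n = 533 | Half-width | All clip, n = 1333 | Half-width |
|---|---|---|---|---|
| 80% | 76.3–83.2% (426) | 3.5 | 77.7–82.1% (1066) | 2.2 |
| 90% | 87.2–92.5% (480) | 2.6 | 88.3–91.6% (1200) | 1.6 |
| 95% | 92.7–96.6% (506) | 2.0 | 93.7–96.1% (1266) | 1.2 |
| 98% | 96.3–99.0% (522) | 1.3 | 97.1–98.7% (1306) | 0.8 |

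The POAF interval is about 1.6 times as wide, as expected from √(1333/533) = 1.58.

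**The case against.** The strongest reply is that little is lost. Section 9.7 already tabulates counts and percentages by group, and section 9.7.1 already foresees an exact confidence interval, so the clip-arm proportion will be visible. That stands, and it limits the point to the choice of inferential statement. Section 9.7.1 does not, however, say which proportion or population the interval describes.

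A reader might infer that the planned test is invalid. It is not: it is a valid test of a null hypothesis that the design has already settled.

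A reader might also infer that the plan throws away about 60% of clip subjects. The documents do not support that. The opening sentence of section 9.6 bases effectiveness analyses on ITT, so an ITT estimate is planned as well, and section 9.7 allows further populations. No sentence assigns endpoint 2 to the POAF population by name; the link comes from reading sections 9.6 and 9.7.2 together. What remains is an inconsistency about which estimate is primary.

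Nor do the documents show that restricting to POAF subjects biases the exclusion rate. They give no relation between closure success and later POAF.

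Finally, the study is described as a hypothesis-generating pilot (section 9.2), and section 9.8 leaves room for a detailed analysis plan. Both are reasons to rate the point low. Neither makes the comparison informative, and the section 9.8 plan is to be written only if needed.

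**Conclusion.** The point holds as a minor one. With control appendages left intact, the between-arm test rejects at 9 clip-arm successes (1.7% of 533 or 0.7% of 1333), so its p-value carries no information on device performance. This assumes a control success rate of about 0%, which follows from section 5.2.1 with adherence; an assumed 5% control rate only moves the threshold to 8.8%.

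Section 9.6 is inconsistent for this endpoint. If the POAF label governs, the primary estimate rests on about 40% of clip subjects, and the half-width grows by 0.5 to 1.3 points across assumed success rates of 80% to 98% (2.0 against 1.2 at 95%). The sample size in section 9.4 is built on a 30-day safety rate and is unaffected, and no success criterion uses this test.

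**What to change.** In section 9.7.1, replace the between-arm test of LAA exclusion with the AtriClip-arm success proportion and its Clopper-Pearson 95% CI as the report for endpoint 2.

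In section 9.6, state that the POAF-primary rule does not apply to this endpoint and that its primary population is the AtriClip arm of the ITT population. Also show the result in all subjects randomised to AtriClip, with non-placements counted as failures. Section 5.2.2 allows the appendage to be left intact after randomisation to the clip, and the attempted-procedure condition in the ITT definition does not settle how such a subject counts. Either denominator is defensible. The intraoperative screening in section 4.2.5 should keep these cases uncommon, though the documents give no rate.

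The cost is a few sentences in sections 9.6 and 9.7.1, or in the detailed plan foreseen in section 9.8. No data collection, patient numbers or power calculation changes.

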In addition, POAF has been shown to have a strong association with perioperative stroke/TIA, increased length of hospital stay, decreased QOL and increased mortality. A 2014 Annals paper from LaPar et al. (LaPar, 2014) evaluated ~50,000 patients undergoing structural heart procedures. For patients with POAF, stroke incidence was 2.6% vs. 1.1% vs. in non-POAF patients at 30-day follow-up, increased ICU time of 48 hours longer, increased hospital LOS of 3 days, and a 25% higher 30-day readmission rate. The total incremental hospital costs associated with POAF was determined to be ~\$9000. Yusuf et al (Yusuf, 2014), reviewed data on over 100,000 cardiac surgery patients in Ontario, Canada over 10 years to examine the rate and predictors of early and late stroke. New-onset POAF was one of the strongest predictors of early stroke with an Odd Ratio of 1.5. Age, history of TIA/stroke, PAD, CHF, and valve surgery were also predictors. The data also showed that increasing CHADS2 scores predicted increased risk of stroke or death among patients with AF vs. those without AF.

An October 2013 JTCVS paper by Chua et al. (Chua, 2013) validated the CHADS2 scoring system as highly predictive for risk of POAF in CABG patients without a history of preoperative AF. Specifically, patients with CHADS2 scores of >2 had a 36% risk of POAF (range of 27-100%).

A more refined scoring system, the CHA2DS2-VASc score, has been validated to define the risk of stroke in AF patients in numerous papers. A CHA2DS2-VASc of \geq 2 estimates an annual risk of stroke of between 4.5-18.2% in patients with AF.

Study Number: CP2015-2 **CONFIDENTIAL** Page 14 of 48

Risks Associated with Initiating Anticoagulation Therapy

Typical hospital protocol for stroke prophylaxis in patients with POAF is the initiation of anticoagulation therapy (AC) within 24 hours of diagnosis. A 2009 Annals paper from (Kasirajan, 2009) et al. identified isolated POAF as adding 2.2 days to hospital length of stay presumably associated with normalization of anticoagulation therapy within therapeutic range. The HASBLED scoring system has been validated in multiple studies to identify the risk of clinically significant bleeding. HASBLED scores of ≥2 have an associated risk of bleeding of between 4.1-19.6% annually.

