4.2.3 Inclusion Criteria

Patients satisfying the following criteria will be considered the screening population and will be eligible for participation:

- 1. Age > 18 years male or female.
- 2. Scheduled for any non-mechanical valve and/or CABG (structural heart) procedure where direct access to the LAA is expected.
- 3. No documented preoperative AF.
- 4. CHA2DS2-VASc score of > 2
- 5. HASBLED score of ≥ 2
- 6. Acceptable surgical candidate, including use of general anesthesia.
- 7. Willing and able to provide written informed consent.
- 8. Female patients must be of non-child bearing potential, or have a negative pregnancy test within 7 days prior to index procedure
- 9. Willing and able to return for scheduled follow-up visits.

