5.0 PROCEDURE

5.1 General Description

Individual centers and investigators will be selected based upon their expertise in the targeted structural heart disease procedures (non-mechanical Mitral Valve Repair/Replacement, Aortic Valve Repair/Replacement, and Coronary Artery By-Pass procedures) as well as proficiency in AtriClip placement.

The term index procedure refers only to the placement/non-placement of the AtriClip (dependent on randomization). All procedures leading up to and after the placement of the AtriClip are considered part of the structural heart procedure and are to be conducted under the discretion of the surgeon in accordance to the hospital's standard of care.

Transesophageal Echocardiography (TEE) with Doppler

Transesophageal echocardiography (TEE) with Doppler must be performed prior to any epicardial surgical intervention. The purpose of the TEE with Doppler is to assess for presence of thrombus. *If a thrombus is present in the left atrium or LAA*, the subject will not be enrolled or randomized into the study and no *AtriClip will be placed*.

The AtriClip LAA Exclusion System must be used only by properly trained and qualified medical personnel in accordance with the Instructions for Use (IFU). Failure to properly follow instructions may result in improper functioning of the device.

Study Number: CP2015-2 CONFIDENTIAL Page 22 of 48

If the subject continues to meet all study eligibility criteria (including intra-operative exclusion criteria), they will be enrolled and randomized. If the subject is randomized to the group to receive the AtriClip LAA Exclusion System placement, the following steps are performed:

Note: A recommended surgical technique is presented below. It is recognized that individual patient anatomic variation, surgical conditions, or surgeon preference may necessitate modifications to the outlined procedures. Regardless, surgeons must adhere to the AtriClip LAA Exclusion System sizing criteria, device selection, and device use instructions as outlined in the IFU.

[figure not shown]

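### Length of stay, OR time and cost are modelled on arm and site only; prespecifying scheduled operation type, age and the two risk scores would probably gain some precision at little cost.

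*Combined protocol and SAP*

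**What the plan says.** Section 9.7.1 states that resource use, including LOS, OR time and total treatment cost, "will be compared between the treatment groups using a two-way analysis of variance (ANOVA) model with procedure group" (the two arms) "and site as fixed effects in the model". No other term is named. The section then adds "These endpoints will also be compared using the two-sided t-test", with a possible switch to a rank-based test if normality fails. Neither test carries covariates, and both drop site. No one of these analyses is named as the main one.

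A covariate list does appear in 9.7.1, but for an optional logistic model of LAA exclusion. Besides site it has "surgical approach (sternotomy, right mini-thoracotomy or other), age, gender" and the two risk scores. Section 9.7.2 extends that model to complications and to thromboembolic and haemorrhagic events, not to resource use.

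Section 4.2.3 makes age, operation ("Scheduled for any non-mechanical valve and/or CABG (structural heart) procedure where direct access to the LAA is expected") and both scores eligibility items. Section 5.1 confirms that the case mix is broad: "non-mechanical Mitral Valve Repair/Replacement, Aortic Valve Repair/Replacement, and Coronary Artery By-Pass procedures". Section 9.5 stratifies randomisation by site, and 4.1 adds blocking by surgeon; nothing balances operation type. Section 9.6 makes the POAF subset primary for health economic endpoints, while also saying that health economic analyses rest on the ITT population.

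**The concern.** The trial mixes coronary, aortic and mitral operations in patients of varying age and risk. It is reasonable to expect that operation type, age and risk score explain part of the variation in OR time, stay and cost. When they are left out of a linear model, that variation stays in the error term and the interval for the treatment difference is wider than it need be. The information to remove it is available before randomisation.

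The primary health economic population adds a second reason. POAF is diagnosed after randomisation, in an unblinded trial, with rhythm monitoring left to hospital practice (4.1). Case mix in that subset is therefore not protected by the randomisation in the way it is among all randomised subjects. Adjusting for measured baseline variables would reduce, though not remove, that weakness.

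**Working it through.** **The plan's own figure.** No sample size or power is stated for LOS, OR time or cost. Section 9.4 sizes the trial on a 30-day event rate in POAF subjects, 12.5% against 6.25%, one-sided 0.05, 80% power, 2:1, continuity corrected. With unpooled variances:

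- n(control) = (1.645 + 0.842)² × (0.125×0.875 + 0.0625×0.9375/2) / 0.0625² = 219.5.
- Continuity corrected: (219.5/4) × [1 + √(1 + 3/(219.5×0.0625))]² = 242.9 control, and twice that, 485.8, AtriClip.

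This matches the stated 243 and 485. Also 2000 × 0.40 = 800, and 728/0.91 = 800, so 533 and 267 POAF subjects are consistent with the plan.

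**Precision for LOS.**

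- From the documents: 533 and 267 subjects (9.4); two-sided 0.05 (9.7).
- Assumed: 80% power for LOS; SD of 5 days; R², the share of within-site variance explained by the four omitted covariates, from 0.05 to 0.25.

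Formulas: SE ratio = √(1 − R²); equivalent sample = 800/(1 − R²); detectable difference = (1.96 + 0.8416) × 5 × √(1 − R²) × √(1/533 + 1/267). The last root is 0.0750, so with R² = 0 the difference is 2.8016 × 5 × 0.0750 = 1.05 days. Power at a true 1.05 days is Φ(2.8016/√(1 − R²) − 1.96).

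| R² (assumed) | SE ratio | Equivalent sample | Detectable difference (days) | Power at 1.05 days |
|---|---|---|---|---|
| 0 | 1.000 | 800 | 1.05 | 80% |
| 0.05 | 0.975 | 842 | 1.02 | 82% |
| 0.10 | 0.949 | 889 | 1.00 | 84% |
| 0.15 | 0.922 | 941 | 0.97 | 86% |
| 0.25 | 0.866 | 1067 | 0.91 | 90% |

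For outcomes that need follow-up, the completers matter: √(1/485 + 1/243) = 0.0786, and 2.8016 × 0.0786 = 0.220 SD unadjusted. The proportional gains are the same.

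**Case mix in the POAF subset.** A simulation of 2,000,000 subjects, 2:1, gave about 40% POAF in controls. One measured risk variable raised the log-odds of POAF by 0.5 per SD and explained 10% or 20% of LOS variance. There was no true treatment effect on LOS. Monte Carlo error is about √(1/533,333 + 1/266,667) = 0.002 SD. The unadjusted difference among POAF subjects was:

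- about 0 if the clip does not affect POAF;
- about 0.005 to 0.02 SD in size if the clip multiplies the odds of POAF by 0.8 to 1.5;
- about 0.04 to 0.06 SD (0.2 to 0.3 days at SD 5) if the clip changes how risk relates to POAF (an added 0.3 on the slope).

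Adjustment brought each to about 0. That is partly by construction, since the only shared cause of POAF and LOS in the simulation was the measured one.

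**The case against.** **The gain may be small and is not documented.** This stands as a limit on size. The support cited from the Introduction, "Age, history of TIA/stroke, PAD, CHF, and valve surgery were also predictors", concerns early stroke, not stay or cost. Requiring minimum scores at entry narrows their range and may lower R². At SD 5 the detectable difference moves by (1.05 − 0.97) × 24, about 2 hours, at R² 0.15, and by about 3.4 hours at 0.25. The Introduction quotes differences of 2 to 5, 2.2 and 3 days, all larger than 1.05. Those figures, however, describe starting anticoagulation or having POAF, not the contrast between arms, and 5.3 leaves anticoagulation to discretion in both arms. If the clip cut anticoagulation starts by 40 percentage points at 2.2 days each (an illustration, not a document figure), the arm difference would be 0.40 × 2.2 = 0.88 days, inside the range where precision matters.

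**Arm plus site matches the stated stratification, and the study is an exploratory pilot not powered on these outcomes.** Both are true. Omitting prognostic covariates from a linear model costs efficiency, not validity.

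**Stronger readings that the documents do not support.**

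- *That covariates will be picked after results are seen.* Section 9.7 allows covariates as needed, but 9.8 provides for a detailed plan before the data are examined. That plan is conditional, so prespecification is permitted but not required.
- *That the unadjusted comparison is biased by chance imbalance.* Chance imbalance is already reflected in its standard error.
- *That adjustment repairs the POAF subset.* It handles only measured baseline differences.
- *That operation type and arm should also go into the logistic models.* Control appendages are left intact (5.2.1), so arm would produce separation in the LAA-exclusion model. For events, 9.4 implies 485 × 0.0625 + 243 × 0.125, about 61 in POAF subjects, too few for up to 20 individual site terms plus the full list. The precision argument for linear models does not carry over to log odds ratios.

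**Conclusion.** The point holds as one of efficiency. The model in 9.7.1 is valid, but it ignores four variables known before randomisation. If they explain 5% to 25% of within-site variance, adjustment lowers the standard error by about 3% to 13%, worth 5% to 33% more patients. The detectable LOS difference would fall from 1.05 days to between 1.02 and 0.91 at an assumed SD of 5 days. The direction is sound if the covariates are prognostic; the size rests on an R² and an SD that the documents do not give. That scheduled operation type is available as a data item is inferred from eligibility, because the schedule of assessments is not visible in the text. A reader might infer that the planned analysis is invalid or that adjustment would make the POAF comparison as good as randomised; neither follows.

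**What to change.** In 9.7.1, make these changes for LOS, OR time and total cost:

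- Prespecify the main model as arm + site + scheduled operation type (isolated CABG, valve, both) + age + CHA2DS2-VASc + HAS-BLED.
- Report the adjusted mean difference with a 95% CI. If the outcome is skewed, use robust or bootstrap standard errors or a suitable generalised linear model.
- Label the t-test and Wilcoxon test as supportive.
- Fix the covariate list before any tabulation by arm.
- Report the same model in the ITT population beside the POAF result. For cost, use a window common to both arms: 4.1 extends one-year follow-up to all POAF subjects and to AtriClip subjects without POAF, but not to controls without POAF.

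Leave the logistic models as they are. The cost is analysis-plan wording, a little more analysis work and five degrees of freedom (two for operation type, one each for age and the two scores) among about 800 POAF subjects. Confirm that the case report form captures scheduled operation type as a coded item.

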4.0 INVESTIGATIONAL PLAN

4.1 Overall Study and Design – Subject Disposition Diagram

Study Number: CP2015-2 CONFIDENTIAL Page 18 of 48

Overall Study and Design - Description

All patients who undergo a valve or CABG (structural heart) procedure with direct visual access to the LAA will be eligible to participate based upon consent and evaluation of the inclusion and exclusion criteria defined in this protocol.

The target patient population includes patients at risk of POAF based on the CHA2DS2-VASc and HASBLED scoring.

Patient must meet all inclusion/exclusion criteria (including intra-operative exclusion criteria) before enrollment or randomization.

During the planned structural heart procedure, the intra-operative exclusion criteria will be assessed. If any intra-operative exclusion criteria are met, the subject will be a screen fail and will not be enrolled or randomized.

To execute randomization, at the time of enrollment, subjects will be assigned a sequential identification number at each site and a corresponding sealed envelope which will be opened in the operating room to reveal the treatment group. Subjects will be randomized 2:1 (2 with AtriClip® to 1 with no AtriClip®). Randomization sequences will be generated by the AtriCure Statistician and will be stratified by site. The subject population will be randomized using a blocking scheme for each surgeon to ensure equal and balanced treatment group allocations and to avoid bias with respect to known or unknown subject variables that could affect the outcome of this study.

Post-index procedure, all subjects will be monitored per the hospital standard of care processes for POAF.

Four (4) treatment arms result:

- Surgery with AtriClip (POAF diagnosed / Institution SoC anticoagulation therapy)
- Surgery with AtriClip (No POAF)
- Surgery with no AtriClip (POAF diagnosed / Institution SoC anticoagulation therapy)
- Surgery with no AtriClip (No POAF)

Subjects will be assessed for AEs related to the placement of the AtriClip and will be instructed to notify the PI of any AEs that occur during the study. All subjects that develop POAF during the hospital stay will be followed for approximately 1 year (365 days) post index procedure. In addition, all the subjects in the AtriClip group that do not develop POAF will also be followed for 365-days post index procedure.

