9.5 Randomization

Upon enrollment, subjects will be assigned a sequential identification number at each site and a corresponding sealed envelope which will be opened prior to the index procedure to reveal the treatment group. Subjects will be randomized 2:1 (2 with AtriClip to 1 anticoagulation therapy and without AtriClip). Randomization sequences will be generated by AtriCure Statistician using SAS version 9.4 (SAS Institute Inc., Cary, North Carolina) and will be stratified by site.

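### Section 4.1 blocks randomisation by surgeon, but section 9.5 and the resource-use ANOVA in 9.7.1 recognise only site; if surgeon blocks are used and surgeons at a site differ, the ANOVA standard error is somewhat too large

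*Combined protocol and SAP*

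**What the plan says.** On allocation, section 4.1 makes two statements in the same paragraph: "Randomization sequences will be generated by the AtriCure Statistician and will be stratified by site", and "The subject population will be randomized using a blocking scheme for each surgeon". Block size is not given. Section 9.5 describes the same process by site: "subjects will be assigned a sequential identification number at each site and a corresponding sealed envelope", with sequences that "and will be stratified by site". It does not mention the surgeon.

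On analysis, section 9.7.1 states: "Resource use such as hospital length of stay, OR time, and total treatment costs will be compared between the treatment groups" by a two-way ANOVA with procedure group "and site as fixed effects in the model". The same endpoints are also to be compared by a two-sided t-test, with a rank-sum test possible if normality fails. Neither of these uses site or surgeon, and the section does not say which comparison is the main one. The optional logistic models in 9.7.1 and 9.7.2 list sites or clusters of sites, not surgeons.

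Section 9.6 makes the POAF subset the primary population for health economic endpoints. Sections 9.7 and 9.8 leave room for unnamed covariates and a later detailed plan, but neither names surgeon.

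**The concern.** A factor used to balance the allocation normally belongs in the analysis. Blocking within surgeon removes surgeon differences from the sampling error of the treatment contrast. If the model omits surgeon, those differences stay in the residual, so the reported standard error describes a less precise trial than the one that was run. Site is already in the ANOVA, so only differences between surgeons at the same site are left out.

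At stake are the interval widths and p-values for the resource endpoints, which serve the second study objective. There is also a question of specification: two statisticians reading 4.1 and 9.5 could build different envelope schedules, and the right model depends on which schedule was used.

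**Working it through.** **The plan's own figure.** No precision or power figure is given for the resource endpoints. The only sample-size figure, in section 9.4, is for a binary rate (12.5% against 6.25%; 243 and 485 completers). It reproduces. The unpooled SE is √(0.125×0.875/243 + 0.0625×0.9375/485) = 0.0239, and the continuity correction is 0.5×(1/243 + 1/485) = 0.0031. Then (0.0625 − 0.0031)/0.0239 − 1.645 ≈ 0.84, a power of 0.80. That figure is not in question here.

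**Inputs from the documents.** Up to 2000 subjects, 2:1; 40% with POAF (9.4); up to 20 sites (9.4) or up to 40 (synopsis); two-sided 0.05 (9.7).

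**Assumptions.** m surgeons of equal size per site (2 to 4); blocks of 6; ρ, the share of within-site variance lying between surgeons, from 0.1 to 0.3; POAF unrelated to arm or surgeon.

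**Formulas.** Set the within-site variance to 1.

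- Residual variance seen by the site-only ANOVA: (1 − ρ) + ρ(1 − 1/m).
- Variance that governs the estimate under surgeon blocking, full set: 1 − ρ.
- The same in a random 40% subset: (1 − ρ) + 0.6ρ(1 − 1/m). Thinning a balanced set to 40% brings back 1 − 0.4 = 0.6 of the imbalance that unblocked allocation would have.
- The same under site-only blocking: (1 − ρ) + ρ(1 − 1/m), equal to the first line.
- R = reported SE / true SE = square root of the ratio of the first line to the relevant later line. Actual type I error = 2[1 − Φ(1.96R)].

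**Example (m = 4, ρ = 0.3).** ITT: √(0.925/0.700) = 1.150. POAF: √(0.925/0.835) = 1.052.

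| m | ρ | R, ITT | R, POAF |
|---|---|---|---|
| 2 | 0.1 | √(0.95/0.90) = 1.027 | √(0.95/0.93) = 1.011 |
| 4 | 0.1 | √(0.975/0.90) = 1.041 | √(0.975/0.945) = 1.016 |
| 2 | 0.3 | √(0.85/0.70) = 1.102 | √(0.85/0.79) = 1.037 |
| 4 | 0.3 | 1.150 | 1.052 |

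With m = 1, or with blocking by site only, R = 1.

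**Check against simulated allocations.** With 2000 subjects in 40 sites × 2 surgeons and 20 × 4, the exact variances gave R = 1.027 and 1.040 (ITT) and 1.010 and 1.015 (POAF) at ρ = 0.1. At ρ = 0.3 they gave 1.099 and 1.144 (ITT) and 1.036 and 1.052 (POAF). Type I error was 0.042 to 0.044 (ρ = 0.1) and 0.025 to 0.031 (ρ = 0.3) in ITT. In POAF it was 0.047 to 0.048 and 0.039 to 0.042. Blocking by site only gave R = 1.00 throughout. Simulations of the outcome itself scatter around these values, reaching 1.16 in ITT and 1.08 in POAF at ρ = 0.3. One small run at 40 × 2 gave 1.067 and 0.990. In POAF at ρ = 0.1 the excess cannot be told from simulation noise.

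**Power in POAF.** For a 0.2 SD effect with 40 sites × 3 surgeons, power with site only against fixed surgeon effects was 0.775 against 0.767 (ρ = 0.1), 0.783 against 0.796 (0.2) and 0.809 against 0.848 (0.3). When surgeons do not differ at all, fixed surgeon effects in POAF raise the SE by about 2% to 3% (1/0.983 to 1/0.974).

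**The case against.** The strongest reply is that this is an exploratory pilot with no power target for resource use, that site already absorbs between-site variation, and that the error is conservative. All of that stands, and it limits the point to a minor one. The allowance for further covariates and a later plan is a weaker defence, since neither names surgeon and a term chosen after the data are seen, in an unblinded trial, is less credible than one fixed now.

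Several stronger readings are tempting, and the documents do not support them.

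- A reader might infer that numbered envelopes in sequence at a site cannot carry surgeon blocks. The text does not say how envelopes are filed or numbered for each surgeon. It is incomplete; impossibility is not shown.
- A reader might infer that the resource tests certainly run below 5%. That needs surgeon blocks to have been used. If they were not, site-only allocation matches the ANOVA and its standard error is valid. The two complaints cannot both apply.
- A reader might take the full-set figures as the size of the problem. The primary population for these endpoints is POAF, where the excess is smaller.
- A reader might expect OR time to suffer most. That is plausible, but nothing in the documents bears on it.
- A reader might want surgeon in the logistic models too. The section 9.4 rates imply about 533×0.0625 + 267×0.125 ≈ 67 events among 800 POAF subjects, fewer than one per surgeon with 80 surgeons.

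**Conclusion.** The point holds conditionally and is minor. Sections 4.1 and 9.5 leave the randomisation stratum unclear, and no planned analysis includes surgeon. If surgeon blocking is used and surgeons at a site differ, the site-only ANOVA overstates the treatment standard error. The excess is about 3% to 16% in ITT; in the primary POAF population it is about 0% to 2% at a surgeon share of 0.1 and 4% to 8% at 0.3. The t-test and rank-sum comparisons omit site as well, so the same point applies to them more strongly.

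The treatment estimate is not biased and type I error is not inflated. The sizes rest on assumed surgeon numbers, block size and variance shares, on a normal outcome in the simulations, and on POAF being unrelated to surgeon and arm.

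**What to change.** 1. Reconcile 4.1 and 9.5: state whether the stratum is surgeon within site or site only. If it is surgeon within site, say how the envelopes are organised for each surgeon. If it is site only, delete the surgeon blocking from 4.1; the ANOVA then needs no change on this account.
2. If surgeon blocking is kept, add surgeon within site to the 9.7.1 model for length of stay, OR time and cost, for example as a random intercept beside procedure group and site. The power figures above used fixed surgeon effects; the random intercept was not simulated.
3. Name that model as the main comparison and the unadjusted t-test or rank-sum test as supportive.
4. Do not require surgeon in the optional logistic models.

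The cost is a clause in 9.5 (or a deletion in 4.1) and a sentence in 9.7.1. Surgeon must be recorded if it defines the block, so no new data are needed. The downside is a slightly more complex model, with little gain in the POAF population if surgeons differ little.
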